1.1 Background and Rationale

As advancements in technology continue, we propose the use of the inControl Diabetes Management Platform for this protocol. It remains a smartphone-based, artificial pancreas platform that automatically controls insulin delivery with an advisory system that generates realtime recommendations for meals, basal rates, bolus calculations and exercise decisions. This cloud based system provides real-time monitoring as well as retrospective analysis on data. The data generated are stored at an inControl Cloud permitting the research team and support networks to observe blood glucose values in real-time if needed. The insulin dosing strategies used in this device are the same strategies currently used in DiAs. This system is identical to the system approved by the FDA in IDE G150221/S002.

In 2009 we initiated one of the first NIH studies dedicated to engineering and clinical testing of closed-loop control (CLC) of type 1 diabetes. Since then, we have achieved key milestones and derived conclusions which enabled further research in this rapidly growing field. Notably, we proposed the idea that the artificial pancreas is not a single all-in-one device but a network encompassing the patient in a digital treatment ecosystem that can offer and alter different treatment modalities in real time depending on the patient's clinical state.

This new notion was reflected in: (1) Our modular engineering design of CLC algorithms, which now allows various treatment modalities to be initiated and swapped without interruption; (2) The Diabetes Assistant (DiAs) – *the first portable CLC hub* using a smart phone to run control algorithms and specifically designed to be operated by the patient, which is now used in a number of outpatient studies in the U.S. and in Europe, and (3) The Unified Safety System (USS Virginia) – the first CLC algorithm *engineered to adapt its mode of operation during the course of every night*, first mitigating after-dinner hyperglycemia and then sliding the patient to a target morning glucose of 120mg/dl, thereby resetting his/her metabolic state for a new day.

Using these technologies, we now propose to compare in a randomized cross-over trial the *long-term efficacy of three treatment modalities* –

SAP=sensor-augmented pump only

USS+SAP (d)=SAP during day and CLC starting at dinner and continuing overnight USS+CLC (d)=24-hour Day and Night Closed Loop Control

We plan to randomize up to 110 patients with type 1 diabetes into two different treatment sequences:

Group A following the sequence $SAP \rightarrow USS+SAP(d) \rightarrow USS+CLC(d) \rightarrow USS+SAP(d)$, and **Group B** following the sequence $USS+SAP(d) \rightarrow USS+CLC(d) \rightarrow USS+SAP(d) \rightarrow SAP$.

These treatment modality sequences are presented in the figure below, and are color coded to match the color-coding of active control modules relevant to each treatment modality presented in Figure 1:

Figure 1: Design of One 11-month Study Session

Each treatment modality will continue for 8 weeks – sufficient time to address the following specific aims:

SA1: Dinner/Night CLC achieved by USS+SAP(d) will be superior to SAP alone in terms of: (1) Improved HbA1c without increasing the risk for hypoglycemia; (2) Reduced incidence and risk for hypoglycemia overnight, and (3) Reduced fear of hypoglycemia and improved diabetes quality of life scores.

SA2: CLC during the day achieved by USS+CLC(d) will preserve the benefits of USS+SAP(d) and will be superior to USS+SAP(d) in terms of: (1) Increased time within target range of 70-180mg/dl during the day; (2) Reduced risk for hypoglycemia, particularly during and after exercise, and (3) Reduced postprandial glucose variability.

SA3: CLC system acceptance evaluated by individual structured interviews and technology acceptance scores will be: (1) Superior, for USS+SAP(d) compared to SAP alone, i.e. adding USS in the evening and overnight will increase patients' acceptance of CLC, and (2) Marginally inferior, for USS+CLC(d) compared to USS+SAP(d); i.e. some patients would prefer SAP alone during the day due to perceived increased system complexity.

1.2 Preliminary Studies

This protocol benefits from extensive study of the Artificial Pancreas system with over 184,000 hours of clinical use with various component structures.

Two recent trials present examples particularly relevant to the proposed clinical studies: Efficacy and Safety of Overnight CLC in Children and Adolescents with Type 1 Diabetes (UVA and Stanford): In 2013, we tested USS Virginia to determine its overnight safety and efficacy in a summer-camp setting: 20 subjects were randomized to CLC using DiAs or SAP (sensor-augmented pump), completing 54 CLC and 52 SAP nights. On nights when DiAs was active for at least 6h, the median time spent in range was 73% for CLC vs. 55% for SAP, p=0.012. Less time was spent below 70mg/dl on CLC vs. SAP, p<0.001; there were **no** hypoglycemic episodes below 60mg/dl on CLC.

Figure 2 presents the data distributions on CLC vs. SAP across several BG ranges. The study concluded that USS Virginia is effective in improving time spent in range, as well as reducing nocturnal hypoglycemia in children and adolescents with type 1 diabetes in a summer camp setting.

Figure 2: % time within several glucose ranges during overnight closed-loop vs. sensor augmented pump in summer camps for children with type 1 diabetes

Overnight Control in Adults with Type 1 Diabetes (UVA and Univ. of Padova): In this study, 10 subjects spent 5 nights on USS Virginia vs. 5 nights on SAP, in random order. CLC resulted in over 30mg/dl lower average BG and over 25% higher time within target range. The mean morning BG on CLC was 119.3mg/dl; thus the USS performed exactly to its design specification–reset BG to 120mg/dl by 7AM (Figure 3).

Figure 3: Glucose distribution during overnight closed-loop (blue) vs. sensor augmented pump (red)

Overnight glucose correlated with glucose control on the next day, r=0.52, p<0.01; peak BG and BG variability during the day (USS inactive) were improved after CLC nights as well. Details are given in the table below.

Main Outcomes of this Study	Sensor-Augmented Pump	Closed-Loop Control	P-value
Average Blood Glucose at 7AM	152.9	119.3	<0.001
Average Blood Glucose (mg/dl)	170.3	139.0	<0.001
Percent time within 70-180mg/dl	59.1%	85.4%	<0.001
Percent time below 70mg/dl	1.56%	0.55%	0.06

These results support the significant glycemic benefits of using USS Virginia overnight and indicate strongly that control during days following well-controlled nights is correspondingly improved. Thus, evaluation of this system is warranted in long-term clinical trials with outcomes gauged by accepted metrics of glucose control.

1.3 Study Objective

Overall, we expect to establish that a distinct overnight CLC modality (USS Virginia) combined with SAP therapy during the day is a viable precursor to future adaptable therapeutic schemes, achieving glycemic control that is superior to SAP alone and optimal balance between system complexity and perceived benefits.

1.4 Closed-Loop Control System

A general description of the Artificial Pancreas Platform devices identified below will be used in the Closed-Loop Control System. New generations of CGMs and insulin pumps with embedded inControl-AP could become available for inclusion in this trial and could be used providing these new developments do not change the core functionality of the system.

For the inControl Platform, (see Figure 4-Panel A):

- inControl Diabetes Management Platform a smart-phone Artificial Pancreas medical platform;
- CGM study CGM connected to the AP using low power Bluetooth communication protocols;
- Insulin Pump insulin pump connected to AP system via wireless Bluetooth.
- Remote Monitoring Server connected to inControl Cloud via 3G or local Wi-Fi network, and
- Modular Closed-Loop Control Algorithm Running on the AP system, which is of Controlto-Range (CTR) class

We have successfully completed a pilot study of the Tandem t:slim X2 with Control-IQ Technology. This pilot study included 5 adults (mean HbA1c 6.5%) using the system between 36-48 hours, and was successfully completed with 86% mean time in target range of 70-180 mg/dL and 2.8% median time below 70 mg/dL. The system maintained connectivity 98% of the intended

time in closed-loop. Given the positive results from this pilot study, we now plan to incorporate t:slim X2 with Control-IQ Technology in this protocol as well.

For the Tandem-G6 configuration, (see Figure 4-Panel B):

The Closed-Loop Control System contained in t-slim X2 with Control-IQ Technology is described in Master File MAF-2032/A003 and has been approved in G170255 and G170267. Control-IQ Technology is derived from inControl previously described in IDE# G160097, G160181, G150240 and G140169/S010. The CLC is an "artificial pancreas" (AP) application that uses advanced closed loop control algorithms to automatically manage blood glucose levels for people with Type 1 Diabetes. The system modulates insulin to keep blood glucose in a targeted range. The system components include the t:slim X2 with Control-IQ Technology and the Dexcom CGM G6 (Fig. 4-B).

Figure 4. AP System Components: Panel A – G4+Roche pump configuration; Panel B – G6+Tandem Control IQ

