2.1 Study Population

We anticipate recruiting up to 110 subjects, ages ≥18 and <70 years. An equal number of males and females will be recruited, and all racial/ethnic groups will be eligible for participation. Based on our experience, we expect that approximately 76% in each arm will complete the study (N=64) and has been increased to account for inclusion of new devices. The randomization will aim to balance the age/gender distributions of the participants in the two groups and to match the groups by baseline HbA1c.

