3.5 Visit 4 – Closed Loop Training Visit

Visit 4 will occur just prior to starting the first session of Closed-Loop Control to ensure that the training is in close proximity to the initiation of the system in closed loop control (for Group B this will occur earlier than Group A).

Visit 3 and 4 may occur concurrently for inControl users. For subjects starting on the Tandem-G6 system, Visit 3 and 4 will be concurrent.

Visit 4 will consist of a ~5-10 hour training session in a transitional setting at a research house, hotel or clinic during which the subject will be trained to use the system to control the study pump, including meal announcement, meal bolusing, exercise, and switching back and forth between Pump (open-loop) mode and Stopped mode. Subjects may be asked to view study materials at home (e.g. User Guides and/or study videos on the Use of the AP System) prior to coming to Visit 4. This visit may shorter than 5-10 hours depending on the subject's proficiency with the system as well as prior experience.

A serum or urine pregnancy test will be collected for all premenopausal women who are not surgically sterile.

Prior to initial use, the system will be initialized with each subject's individual parameters, including carbohydrate ratio, correction factor, and basal rate pattern.

Study team members will train the subject in performing specific tasks including the following:

- The study team will confirm the pump parameters entered in the system with the subject.
- How to switch the system between Pump mode (open-loop, preprogrammed basal insulin delivery) and Stopped mode depending on circumstances. For the Tandem-G6 system, this will consist of turning Control-IQ off.
- How to calibrate the CGM unit during the study.
- How to access the CGM trace on the user interface.
- How to activate the meal screen of the system any time insulin will be given with a meal or any time additional correction insulin is desired.
- How to inform the system of hypoglycemia treatment on the user interface.
- What to do in when engaging in strenuous exertion
- How to perform blood ketone testing and perform rescue therapy actions with the glucagon kit

- The subject will be assessed for understanding of the system interface and how to react to safety/alert messages.
- The subject will be given a AP system User Guide relevant to their system (Appendix A-10) as a reference.

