6.1 Analysis Plan

Statistical Analysis: The overall analysis will follow Intention-to-treat approach and will use Generalized Linear Mixed Models (e.g. those available in IBM SPSS) including fixed factors following the factorial designs presented in study figure for the specific aims listed below, and random effects reflecting patients' attrition rate.

Metrics:

- (i) Five HbA1c determinations approximately 10 weeks apart;
- (ii) Eight-week sequences of CGM data accompanied by BG self-monitoring readings and recording of the timing of events such as meals and exercise through the GUI
- (iii) Psychometric questionnaires administered concurrently with HbA1c, and
- (iv) Individual structured interview and qualitative/quantitative technology acceptance assessments. CGM data will be used to compute established metrics of risk for hypoglycemia, e.g. the Low BG Index (LBGI), glucose variability, and BG dynamics, as presented in our review of statistical tools for CGM data analysis.

Primary Hypothesis by Specific Aims of the Study

Specific Aim 1: Overnight CLC achieved by USS+SAP(d) will be superior to SAP alone in terms of: (1) Improved HbA1c without increasing the risk for hypoglycemia; (2) Reduced incidence and risk for hypoglycemia overnight, and (3) Reduced fear of hypoglycemia and improved diabetes quality of life scores.

Specific Aim 2: CLC during the day achieved by USS+CLC(d) will preserve the benefits of USS+SAP(d) and will be superior to USS+SAP(d) in terms of: (1) Increased time within target range of 70-180mg/dl during the day; (2) Reduced risk for hypoglycemia during and after exercise, and (3) Reduced postprandial glucose variability.

Specific Aim 3: CLC system acceptance evaluated by an individual structured and technology acceptance scores will be: (1) Superior, for USS+SAP(d) compared to SAP alone, i.e. adding USS overnight will increase patients' acceptance of CLC, and (2) Marginally inferior, for USS+CLC(d) compared to USS+SAP(d); i.e. some patients would prefer SAP alone during the day due to perceived increased system complexity.

Primary Outcomes

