6.2 Sample Size

Sample Size Determination is based on our pilot studies of overnight CLC. We conservatively estimate that the effect size of USS+SAP(d) vs. SAP will be $f \ge 0.2$. Power calculations (G*Power 3) assuming $\alpha = 0.01$, 90% power, correlation of 0.4 between the repeated measures, and attrition of up to 31% yield a sample size of **N=110** subjects to be randomized at baseline, with N=76 subjects completing the study. For SA2 using USS+CLC(d), our pilot data with this same system during the day indicate a larger effect size f=0.3. For SA-3, the expected effect size is f=0.35-0.4 based on our previous interviews. Thus, a sample size that is adequate for SA-1 will have adequate power to address SA-2 and SA-3 as well.

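### No rule keeps a subject on one AP system and one CGM generation, and read literally Tandem subjects change sensor inside the CGM-based SA1 contrast; section 6.1 has no system term or by-system analysis

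*Combined protocol and SAP*

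**What the plan says.** Section 1.4 describes inControl (G4 with the Roche pump in Figure 4, Panel A) and then states that "we now plan to incorporate t:slim X2 with Control-IQ Technology in this protocol as well", using the Dexcom G6 (Panel B). Newer devices are also foreseen: "New generations of CGMs and insulin pumps with embedded inControl-AP could become available for inclusion in this trial and could be used". The condition attached is that they leave the system's core functionality as it is. The section does not say who judges that condition or by what test.

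Section 2.1 says of the sample that it "has been increased to account for inclusion of new devices". Section 6.2 has no device input: "Sample Size Determination is based on our pilot studies of overnight CLC".

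On which device a subject wears, and when:

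- Section 3.5: "For subjects starting on the Tandem-G6 system, Visit 3 and 4 will be concurrent". This refers to the starting system only.
- Section 3.9 (SAP) names Dexcom G4 as the study CGM. It adds that subjects on Tandem-G6 in the AP phases use their home pump during SAP, but says nothing about their sensor.
- Section 3.11 mentions inControl subjects on Dexcom G5, a third generation.

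Section 6.1 specifies a mixed model "including fixed factors following the factorial designs presented in study figure". The figure is not shown, but section 1.1 describes it as presenting the treatment sequences. No system or CGM term, by-system estimate or device sensitivity analysis is named. The SA1 primary outcome is CGM time below 70 mg/dL on USS+SAP(d) against SAP, without an increase in HbA1c. The SA2 primary outcome is daytime time in 70-180 mg/dl on USS+CLC(d) against USS+SAP(d).

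**The concern.** In a crossover each subject is his or her own control, so a device that stays the same throughout drops out of the contrast. A device that changes between the compared phases does not.

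Sections 1.4 and 3.9, taken together, produce such a change for Tandem subjects: G4 in SAP, G6 in USS+SAP(d). If the two sensors differ in how much time they report below 70 mg/dL, that difference is added to the SA1 treatment effect. Sequence randomisation does not remove it, because it is tied to the modality and not to the period: it has the same sign whether SAP comes first (Group A) or last (Group B).

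Two smaller issues follow from the same gap. A device change between a subject's AP phases enters that subject's SA2 contrast. And if the modality effect differs between systems, the planned analysis has nothing that would show it.

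**Working it through.** **Stated sample size.** Inputs from section 6.2: f = 0.2, alpha 0.01, power 90%, correlation 0.4, attrition 31%. Repeated-measures F test, within factor, m = 4 phases: lambda = f²·N·m/(1 − 0.4). The smallest N is 75, or 76 in two equal groups, with power 0.909 at 76. For attrition, 110 × 0.69 = 75.9. The plan's 76 and 110 reproduce. With four system-by-sequence cells, power at 76 is still 0.909.

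**Sensor change inside SA1.** Assumptions that the documents do not give: share on Tandem w; sensor difference s, in SD units of a single-phase value.

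- The mean shift in SA1 is w·s, in both sequences.
- Paired difference of two phases: SD = √(2 × (1 − 0.4)) = 1.095.
- Noncentrality with no true effect: w·s/1.095 × √76. The two-sided 1% critical value on 75 df is 2.643.
- The small extra variance from a sensor difference present in only some subjects is ignored.

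| w | s (SD) | Shift (SD) | Noncentrality | Chance of a significant result with no true effect |
|---|---|---|---|---|
| 25% | 0.2 | 0.05 | 0.40 | 1.6% |
| 50% | 0.2 | 0.10 | 0.80 | 3.7% |
| 75% | 0.2 | 0.15 | 1.19 | 8.0% |
| 25% | 0.4 | 0.10 | 0.80 | 3.7% |
| 50% | 0.4 | 0.20 | 1.59 | 15% |
| 75% | 0.4 | 0.30 | 2.39 | 40% |

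If SAP is compared with the mean of the two USS+SAP(d) phases, the variance is 0.6 × 1.5 = 0.9 in place of 1.2, and the two 50% rows become 4.7% and 22%.

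The sign of s is unknown. If it works against the treatment, the planned 0.4 SD (d = 2f) falls to 0.30 or 0.20 SD at w = 50%. Power of the same paired test then falls from 70% to 40% or 15%.

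**Device change during the AP phases.** Sequences: A = SAP, U, C, U; B = U, C, U, SAP, where U is USS+SAP(d) and C is USS+CLC(d). SA2 = C minus the mean of the two U phases. A step of size b after a given phase shifts that subject's SA2 contrast by:

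| Change after phase | Group A | Group B |
|---|---|---|
| 1 | 0 | +b/2 |
| 2 | +b/2 | −b/2 |
| 3 | −b/2 | 0 |

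Each column sums to zero. If entry is evenly staggered, so that a change date falls equally often after each phase, the mean SA2 shift is zero in each group.

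**What a system-by-modality term can detect.** SE = √(1.2 × (1/n1 + 1/n2)), two-sided 0.05, 76 completers. Differences between the systems' effects are assumed.

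| Split | SE | Power, difference 0.2 SD | Power, difference 0.4 SD |
|---|---|---|---|
| 19 / 57 | 0.290 | 11% | 28% |
| 38 / 38 | 0.251 | 13% | 36% |

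**The case against.** The strongest reply is that the plan treats system as an attribute of the subject. Sections 3.9 and 3.11 speak of Tandem-G6 subjects and inControl subjects, closed-loop training takes place once, and the washout visits describe no retraining on another system. The G4 in section 3.9 may be text not updated when Tandem was added, and section 1.5.2 says only study CGM for SAP. This stands as far as it goes: switching between AP systems is not shown to be planned. But no rule forbids it, and nothing in the text gives Tandem subjects a G6 in SAP.

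The HbA1c part of SA1 does not depend on the sensor, and if system and sensor stay fixed through the AP phases, SA2 is unaffected. Both points stand.

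A reader might infer more than the documents support:

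- *That devices may enter without restriction.* Section 1.4 sets the core-functionality condition, though it does not address differences in sensor measurement.
- *That the device mix by itself distorts the pooled result.* A stable system's main effect cancels within subject. The mix matters only if the treatment effect differs by system. No per-system effect is given, and section 1.4 says that Control-IQ derives from inControl, which makes similar effects plausible.
- *That system must be a balancing factor.* Section 2.1 says "The randomization will aim to balance the age/gender distributions of the participants in the two groups and to match the groups by baseline HbA1c", with no mention of system. With a stable system, balancing it between sequences would gain almost nothing.
- *That SA2 is biased by device changes.* The shifts average out under even staggered entry. They are mainly noise unless changes are uneven or selective.
- *That the sample size is wrong.* It reproduces, with or without system as a factor.

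**Conclusion.** The concern holds in a limited form, as a low-cost improvement. The documents establish that two systems are pooled, that three CGM generations appear in the text, that no rule fixes system or sensor per subject, and that the analysis ignores both. Read literally, sections 1.4 and 3.9 place a sensor change inside the primary SA1 contrast, in the same direction in both sequences.

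The size is not known. The false-positive rate of about 3.7% to 15% against 1% rests on an assumed 50% Tandem share, an assumed sensor difference of 0.2 to 0.4 SD and a paired test in 76 completers. If the sensors agree, or if Tandem subjects in fact wear one generation throughout, this bias is zero. The SA2 issue is mainly added noise, and a difference in effect between systems is possible but not shown.

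**What to change.** 1. **Sections 1.4, 3.9 and 3.11.** Reconcile them so that each subject has one AP system for all AP phases and the same CGM generation in all four phases, SAP included, with new generations used only for subjects not yet randomised. The assignment must be made before the first phase, because Group A's SAP precedes its pump and closed-loop training (section 3.2). If a change is unavoidable, record system and CGM by phase and run a sensitivity analysis that excludes subjects whose device changed.
2. **Section 6.1.** Add a system-by-modality term to the SA1 and SA2 models and report each contrast by system beside the pooled estimate. Label these results descriptive, since the power to detect a difference is only about 11% to 36% under the assumptions above.

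Cost: protocol and SAP wording, one or two degrees of freedom, and keeping older sensors and pumps available until current subjects finish. The planned sample size need not change.
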